#### 4.3. Interim Analyses

Not applicable

Sponsor:	ObsEva		
Protocol:	19-OBE2109-005		
Document Version No.:	1.0	Document Date:	18-MAY-2021

#### 4.4. Subject Disposition

A tabulation of subject disposition will be presented by treatment group and overall, for randomized subjects in the main study, including :

- Number of subjects randomized in the main study,
- Number of subjects who completed the main treatment period until Month 6
- Number of subjects who signed consent form for the extension study,
- Number of subjects who discontinued the study between informed consent for extension study and the first day of study drug in extension period,
- Number of subjects who received at least one dose of study drug in the extension study,
- Number of subjects who completed the extension treatment period until Month 12
- Number of subjects who discontinued the extension treatment period prior to Month 12, and reasons for extension treatment discontinuation
- Number of subjects who entered the extension follow-up period
- Number of subjects who discontinued the extension follow-up period, and reasons for the extension follow-up period discontinuation
- Number of subjects who completed the extension study (complete the extension treatment period and the extension follow-up period)

The number of subjects included in the extension study by country and by site will be also provided.

The number in each subject population for analysis will be presented by treatment group and overall, for Extension Safety Analysis Set. The number of subjects who completed each visit of the extension study will be summarized by treatment group and overall, for the Extension Safety Analysis Set.

The following listings will be presented:

- Study completion information, including the reason for premature study withdrawal, if applicable;
- Inclusion/exclusion criteria;
- Subject inclusion in each of the analysis sets (Extension Safety Analysis Set and Follow-up Extension Safety Set) and reasons for exclusion

#### 4.5. **Demographic and Baseline Characteristics**

Baseline, demographic and medical history information will be analyzed by treatment group and overall, for the Extension Safety Analysis Set.

Sponsor:	ObsEva		
Protocol:	19-OBE2109-005		
Document Version No.:	1.0	Document Date:	18-MAY-2021

No formal statistical comparisons will be performed.

### 4.5.1. **Demographics**

Demographics and baseline characteristics recorded at baseline in the main study will be summarized by treatment group and overall using descriptive statistics.

Demographics and baseline data include Age (years), Gender, Ethnicity, Race, Height (cm), Weight (kg), Body Mass Index (kg/m2), Systolic Blood Pressure (mmHg), Diastolic Blood Pressure (mmHg), Heart Rate (beats/minute), QTc interval (Fridericia) (ms).

BMI is auto-calculated, defined as: Weight (kg)/(Height(m)\*Height(m)).

Demographic and Baseline data will be provided in data listings.

### 4.5.2. Baseline Disease Characteristics

For the 4 treatment groups (as detailed in section 4.2.1), the following parameters, recorded at baseline in the main study, will be calculated as described in section 4.5.2 of the SAP of the main study.

- Baseline Dysmenorrhea (DYS)
- Baseline Non-Menstrual Pelvic Pain (NMPP)
- Baseline analgesic use.
- The average duration of the two baseline menstrual cycles (days)
- The number and percentage of subjects with Normal, Abnormal, Abnormal clinically significant (or Not Assessable) results for Physical Examination, Gynecological Examination, Breast Examination, Mammography, Endometrial Biopsy and PAP Smear assessments at baseline.
- Transvaginal ultrasound data (i.e., presence of ovarian endometrioma with a diameter of 7 cm or greater, uterus length, width, and depth in mm and corresponding calculated uterine volume in cm3 (using the prolate ellipsoid formula [L x H x W x 0.523]), endometrium thickness in mm, and presence of any uterus, left ovary or right ovary abnormality).

Only for subjects receiving Placebo in the main study, these baseline characteristics will be described as the definition of the second baseline (section 4.2.11 of this SAP):

• The number and percentage of subjects with Normal, Abnormal, Abnormal clinically significant (or Not Assessable) results for Physical Examination, Gynecological Examination, Breast Examination, Mammography (if required), Endometrial Biopsy (if required), for baseline 2.

Sponsor:	ObsEva		
Protocol:	19-OBE2109-00	5	
Document Version No.:	1.0	Document Date:	18-MAY-2021

• Baseline 2 Transvaginal ultrasound data (i.e., presence of ovarian endometrioma with a diameter of 7 cm or greater, uterus length, width, and depth in mm and corresponding calculated uterine volume in cm3 (using the prolate ellipsoid formula [L x H x W x 0.523]), endometrium thickness in mm, and presence of any uterus, left ovary or right ovary abnormality).

Baseline Disease Characteristics will be reported in listings.

## 4.5.3. Medical History

Medical history, recorded at baseline in the main study, will be summarized by System Organ Class and Preferred Term using the Medical Dictionary for Regulatory Activities (MedDRA), by treatment group and overall.

Medical history will be summarized by subject incidence rates; therefore, a subject contributes only once to the count for a given medical history (SOC or preferred term).

Medical history will be reported in a listing.

## 4.5.4. Endometriosis History

For the 4 treatment groups (as detailed in section 4.2.1), the following parameters, recorded at baseline in the main study, will be calculated as described in section 4.5.2 of the SAP of the main study.

Time since first medical diagnosis/treatment, first surgical diagnosis and most recent surgical diagnosis in years defined as (randomization date – date of diagnosis)/365.25 will be summarized.

Presence within 2 months before screening and ongoing symptoms at baseline of the main study for the following symptoms will be summarized, by treatment group and overall: Dyspareunia, Dyschezia, Dysuria, Adenomyosis, Rectovaginal endometriosis nodes.

Endometriosis History will be reported in a listing.

#### 4.6. **Efficacy Evaluation**

Following the early termination of the study and due to the number of subjects randomized being substantially lower than the target number if the study had been fully enrolled, no efficacy analyses are planned.

Efficacy data from eDiaries, eCRF, quality of life questionnaires and other ePROs questionnaires will be reported in listings.

Sponsor:	ObsEva		
Protocol:	19-OBE2109-00	5	
Document Version No.:	1.0	Document Date:	18-MAY-2021

#### 4.7. **Pharmacokinetic Evaluations**

Following the early termination of the study and due to the number of subjects randomized being substantially lower than the target number if the study had been fully enrolled, no pharmacokinetic analysis is planned.

### 4.8. Safety Analyses

Safety analyses will be conducted using the Extension Safety Analysis Set.

### 4.8.1. Extent of treatment exposure and compliance on the extension study

### 4.8.1.1. Extent of treatment exposure in the extension study

Duration of treatment (weeks) will be summarized for each treatment group. Duration is defined as: [(date of last extension treatment administration as described in section 4.2.12) - (date of first administration in extension as collected in eCRF) +1] / 7.

Time on extension study (weeks) will be summarized for each treatment group, defined as: [(end of extension study date as described in section 4.2.12) – (date of first administration in extension as collected in eCRF) +1.]/7

Exposure data will be reported in listings.

## 4.8.1.2. Compliance in the extension study

Lingazolix/Placebo Grey blister (200 mg or matching placebo), Lingazolix/Placebo Pink blister (75 mg or matching placebo) and Add-back therapy compliances from the study treatment accountability page will be summarized on the extension treatment period by treatment group.

If Lingazolix/Placebo and Add-back therapy compliances from accountability data are missing, compliance will be computed from daily diary data:

Compliance will be computed as the number of days with pink tablet/grey tablet/red capsule taken \*100 divided by the number of days in the period (Month 12 visit date/discontinuation date - Month 6 visit date ). Data from "Today" will be used primarily. If data from today is missing, date from "Yesterday" will be considered. If the e-diary is not completed for a day (neither "Today" nor "Yesterday), it will be assumed that no drug was taken on that day.

Study treatment overdose and misuse will be reported in a listing.

Sponsor:	ObsEva		
Protocol:	19-OBE2109-005		
Document Version No.:	1.0	Document Date:	18-MAY-2021

Compliance will be reported in a listing.

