## 4.2.12. Last extension treatment administration date, End of extension Study date and Period definitions

The last extension treatment administration date will be defined as the date from the treatment termination reported in the extension period eCRF page. If this date is missing, the last date with a drug intake in the eDiary that is inferior or equal to Month 12 visit or the last available date with a drug intake in the eDiary if the subject discontinued the extension treatment will be used.

For subjects who entered the extension, the end of the extension study date will be the last assessment date in the extension study defined as last assessment recorded in the eCRF (excluding end date of adverse events and concomitant medications) or ediary date.

Note:

- For summaries by visit (efficacy or safety), the Month 6 assessments will be included in the main study analyses. For Adverse Events, Concomitant Medications and Daily diaries data collected on the Month 6 date will be part of the extension for subjects entering the extension study, and will be part of the main Follow-up period for subjects entering the main study follow-up period.
- For Adverse Events, Concomitant Medications and Daily diaries, data collected on the Month 12 date will be part of the Extension Follow-up period for subjects entering the Extension follow-up period.

The extension treatment period will be defined as Month 6 up to (Month 12 date -1) or treatment discontinuation date.

The extension follow-up period will be defined as the Month 12 date or (treatment discontinuation date+1) up to the extension follow-up end date (for subjects who entered the extension follow-up).

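### The diary-based compliance fallback has a denominator one day short for women who stop early, if its undefined discontinuation date is the last treatment day of SAP 4.2.12

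*SAP*

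**What the plan says.** SAP 4.8.1.2 takes compliance from the accountability page first. The diary is a fallback: if the "compliances from accountability data are missing, compliance will be computed from daily diary data". The numerator is given as "Compliance will be computed as the number of days with pink tablet/grey tablet/red capsule taken", multiplied by 100. The denominator, described as the length of the period in days, is "Month 12 visit date/discontinuation date - Month 6 visit date". One subtraction serves completers and early stoppers alike.

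SAP 4.2.12 sets the boundaries of that period, and it treats the two groups differently: "The extension treatment period will be defined as Month 6 up to (Month 12 date -1) or treatment discontinuation date". The next period begins accordingly: "The extension follow-up period will be defined as the Month 12 date or (treatment discontinuation date+1"). The same section adds: "The last extension treatment administration date will be defined as the date from the treatment termination reported in the extension period eCRF page".

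SAP 4.8.1.1, just before the compliance section, defines treatment duration as the last extension administration date minus the "date of first administration in extension as collected in eCRF) +1] / 7".

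**The concern.** The number of days from one date to another, counting both ends, is the difference plus one. For completers the plus one is not needed, because the closing date (the Month 12 visit) is not a dosing day. For early stoppers SAP 4.2.12 puts the closing date inside the treatment period, so it is needed, and 4.8.1.2 leaves it out.

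The result would be compliance above 100% in fully adherent women, and a reported 100% in women who missed one dose. The error always runs upward on this reading, is largest after short treatment, and touches only early stoppers, so completers and early stoppers in the same table would be measured on different scales. The study itself was terminated early (SAP 1.2), and SAP 2.1 reports all subjects whatever their treatment duration, so the early-stop branch cannot be dismissed as purely theoretical.

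**Working it through.** The documents state no compliance figure to reproduce, so the completer branch serves as the anchor.

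**Inputs**
- First extension dose: at the Month 6 visit, from the new kits (Protocol 10.2.1.1); nominal Day 169. SAP 4.2.12 assigns diary data from that date to the extension, so the day counts in the numerator.
- Last dose for completers: the day before the Month 12 visit (Protocol 10.2.1); Month 12 is nominal Day 337.
- Last treatment day for early stoppers: the treatment discontinuation date, with follow-up starting the next day (SAP 4.2.12).
- Link between that date and the last dose: SAP Table 4 places the Month 1 follow-up visit 28 days after treatment discontinuation, and Protocol 10.2.2.1 places it 28 days after the last IMP intake for early-discontinued subjects. Read together, the two dates are the same.

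**Completers**
- Doses: 336 - 169 + 1 = 168.
- Denominator in 4.8.1.2: 337 - 169 = 168.
- Compliance with every dose taken: 168/168 = 100%.
- Exposure in 4.8.1.1: 336 - 169 + 1 = 168 days. The two sections agree.

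**Early stoppers**

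Let k be the dosing days from the Month 6 visit to the last dose, both counted, and let the discontinuation date be the last dosing day.
- Discontinuation day = 169 + k - 1.
- Doses with full adherence = k; exposure days in 4.8.1.1 = k.
- Denominator in 4.8.1.2 = (169 + k - 1) - 169 = k - 1.
- Compliance with every dose taken = 100 × k/(k - 1).
- With exactly one dose missed: 100 × (k - 1)/(k - 1) = 100% for any k of 2 or more, against a true value of 100 × (k - 1)/k.

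| k (days) | Discontinuation day | Stated denominator | All doses taken, as stated | One dose missed, as stated | One dose missed, true value |
|---|---|---|---|---|---|
| 7 | 175 | 6 | 7/6 = 116.7% | 100% | 6/7 = 85.7% |
| 28 | 196 | 27 | 28/27 = 103.7% | 100% | 27/28 = 96.4% |
| 56 | 224 | 55 | 56/55 = 101.8% | 100% | 55/56 = 98.2% |
| 84 | 252 | 83 | 84/83 = 101.2% | 100% | 83/84 = 98.8% |
| 140 | 308 | 139 | 140/139 = 100.7% | 100% | 139/140 = 99.3% |

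At k = 1 the denominator is zero and compliance is undefined.

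**If a later visit date is meant instead**

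Let that visit fall g days after the last dose (g is an assumption; the documents give none). The denominator is then k - 1 + g.
- g = 1: 28/28 and 84/84, both 100%.
- g = 3: 28/30 = 93.3%; 84/86 = 97.7%.
- g = 7: 28/34 = 82.4%; 84/90 = 93.3%.

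So the stated formula is right for early stoppers only when the date used is exactly one day after the last dose.

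**The case against.** The strongest reply is that 4.8.1.2 says only discontinuation date, without the word treatment, and sets it beside the Month 12 visit, which is a day without dosing. Early stoppers undergo the Month 12 procedures at a withdrawal visit (Protocol 10.7.2; SAP 4.2.7), so a visit date is a possible parallel. If that visit came the day after the last dose, the formula would be correct, and adding one would turn 28/28 into 28/29 = 96.6%. SAP 4.2.12 also does not say outright that a dose is taken on the discontinuation date; its sentence on the last dose speaks of treatment termination.

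Part of this stands. The date is not named, so the percentages above are conditional. But the denominator is meant to be the length of the treatment period, and 4.2.12 closes that period on the treatment discontinuation date. The visit-date reading fits that definition poorly and gives a correct figure for one gap only.

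A reader might infer that the exposure formula in 4.8.1.1 flatly contradicts the compliance formula because one has the plus one and the other lacks it. The documents do not support that. Exposure runs between administration dates and compliance between visit or discontinuation dates, and for completers the two differ in form yet both give 168. The mismatch arises only in the early-stop branch, under the 4.2.12 meaning of the date.

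It is also fair that a day with no diary entry, either that day or the next, counts as no drug taken. This pulls compliance down, so not every affected woman would exceed 100%. It does not restore the missing day in the denominator.

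**Conclusion.** The formula is wrong as written for women who stop early, on the reading that best fits the SAP's own period definition. The denominator is one day short, which adds 3.7 percentage points for a fully adherent woman at 28 days and 0.7 at 140. The completer branch is correct and should not be touched. Confidence is moderate, because the result assumes that the discontinuation date is the treatment discontinuation date and the last dosing day, and that the first extension dose falls on the Month 6 visit.

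The importance is minor. The formula applies only where accountability compliance is missing, and accountability is scheduled at every treatment visit (Protocol Appendix A). Compliance is summarised and listed only; no hypothesis is tested (SAP 4.2.5), and neither analysis set in SAP 3.1 depends on a compliance threshold. A reader might infer from the early termination that a large share of women is affected, or that safety conclusions could shift. The documents give no count of early stoppers or of missing accountability data, and nothing in them ties a safety conclusion to this figure.

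**What to change.** Either of two changes to SAP 4.8.1.2 would do.

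1. State that the date is the treatment discontinuation (last dose) date of 4.2.12, and split the denominator: Month 12 visit date minus Month 6 visit date for completers; treatment discontinuation date minus Month 6 visit date plus 1 for early stoppers. Full adherence then gives exactly 100% at every duration. A blanket plus one would be wrong, because completers would score 168/169 = 99.4%.
2. More simply, use the dates of 4.8.1.1 for everyone: last extension administration date minus first extension administration date plus 1. This gives the same result when the first dose is on the Month 6 visit and a completer's last dose is the day before Month 12. It also holds if a remote visit (Protocol 5.7) separates the visit from the first dose. Its one limit is that doses missed at the very end of treatment fall outside the period.

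The cost is one sentence and one term in a formula, with no new data. The date must be named in the same edit, since adding a day to a visit-based date could introduce an error of its own.

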# Cytel

## Statistical Analysis Plan

Sponsor:	ObsEva		
Protocol:	19-OBE2109-005		
Document Version No.:	1.0	Document Date:	18-MAY-2021

IMP Intake Data:

- IMP Intake data from "Today" will be used primarily. If data from "Today" is missing, data from "Yesterday" of the following day will be considered

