## 7.1. Appendix A: Mapping rules for ediary data

Table 5 Mapping Rules for

Device

Cas e #	impacte d visit	Patient status	Schedul e of daily diary	impact on data	Cytel action on IMP intake data	Cytel action on Menstrual data	Cytel mapping	cut off date (from eCRF)
1	Month 6	patient was included in EXT	remain ed in MAIN TREAT MENT (due to Covid remote visit or to site error in diary comple tion)	data present in the Main datasets should be considere d for the analysis of the extension study	mapping	n/a	from MAIN TREAT to EXT TREAT	First IMP intake in EXT

Sponsor:	ObsEva		
Protocol:	19-OBE2109-00	5	
Document Version No.:	1.0	Document Date:	18-MAY-2021

2	Month 6	patient was included in EXT	resched uled to MAIN FU (due to site error in diary comple tion)	data present in the Main datasets should be considere d for the analysis of the extension study	n/a - missing in final DB	n/a	from MAIN FU to EXT TREAT	First IMP intake in EXT
3	Month 6	patient entered MAIN FU	resched uled to EXT TREAT MENT (site error in diary comple tion)	data present in the Extension datasets should be considere d for the analysis of the Main study	"Is the subject eligible to the 6 months treatment free follow-up?" is YES> delete answers to YIMPI and IMPI	n/a	from EXT TREAT to MAIN FU	MONTH 6 visit date

Sponsor:	ObsEva		
Protocol:	19-OBE2109-00	5	
Document Version No.:	1.0	Document Date:	18-MAY-2021

4	Month 6	patient entered MAIN FU	remain ed in MAIN TREAT MENT (due to Covid remote visit or to site error in diary comple tion)	Data regarding IMP intake will be present for this period	"Is the subject eligible to the 6 months treatment free follow-up?" is YES> delete answers to YIMPI and IMPI	n/a	n/a - remain in MAIN DB	MONTH 6 visit date
5	Month 6	whatever status: DUPLICATE ENTRIES	patient entered diary data in both Main and Extensi on studies each day	duplicate s data will be present across the datasets	CASE by CASE review	- cleaning need	ded	

Sponsor:	ObsEva			
Protocol:	19-OBE2109-005			
Document Version No.:	1.0	Document Date:	18-MAY-2021	

6	Day 1	patient entered MAIN TREATMENT	remain ed in SCREEN ING (due to site error in diary comple tion)	Data regarding IMP intake will not be present for this period and data regarding menstrua I periods will be present	n/a - missing in final DB	delete the answers to "is it your Menstrual period?" and start date questions, if any	n/a - remain in MAIN DB	First IMP intake in MAIN

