## Table 6 Mapping Rules for Signant Health Device

Cas e #	impacted visit	Patient status	Schedule of Signant Health daily diary	impact on data	Cytel action on IMP intake data	Cytel action on Menstrual data	Cytel mapping	cut off date (from eCRF)
1	Month 6	patient was included in EXT	remained in MAIN TREATMENT (due to Covid remote visit or to site error in diary completion)	data present in the Main datasets should be considered for the analysis of the extension study	mapping	n/a	from MAIN TREAT to EXT TREAT	First IMP intake in EXT
2	Month 6	patient was included in EXT	rescheduled to MAIN FU (due to site error in diary completion)	data present in the Main datasets should be considered for the analysis of the extension study	n/a - missing in final DB	n/a	from MAIN FU to EXT TREAT	First IMP intake in EXT
3	Month 6	patient entered MAIN FU	rescheduled to EXT TREATMENT (site error in	data present in the Extension datasets should be	delete answers to Yesterday IMP intake and to Today IMP intake if any	n/a	from EXT TREAT to MAIN FU	MONTH 6 visit date

Sponsor:	ObsEva			
Protocol:	19-OBE2109-005			
Document Version No.:	1.0	Document Date:	18-MAY-2021	

			diary completion)	considered for the analysis of the Main study				
4	Month 6	patient entered MAIN FU	remained in MAIN TREATMENT (due to Covid remote visit or to site error in diary completion)	Data regarding IMP intake will be present for this period	delete answers to Yesterday IMP intake and to Today IMP intake if any	n/a	n/a - remain in MAIN DB	MONTH 6 visit date
5	Day 1	patient entered MAIN TREATMENT	remained in SCREENING (due to site error in diary completion)	Data regarding IMP intake will not be present for this period and data regarding menstrual periods will be present	n/a - missing in final DB	delete the answers to "is it your Menstrual period?" and start date questions, if any	n/a - remain in MAIN DB	First IMP intake in MAIN
6	Any Monthly visit of the Main	patient in MAIN TREATMENT	Set-up in screening period (due to site error in	Data regarding IMP intake will not be present for this period	n/a - missing in final DB	delete the answers to "is it your Menstrual period?" and	n/a - remain in MAIN DB	First IMP intake in MAIN

Sponsor:	ObsEva			
Protocol:	19-OBE2109-005			
Document Version No.:	1.0	Document Date:	18-MAY-2021	

Treatmen	diary	and data	start date	
t period	completion)	regarding	questions, if any	
		menstrual		
		periods will be		
		present		

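### The fallback diary compliance in SAP 4.8.1.2 scores days on which drug intake could not be recorded (mapping case 2) as missed doses

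*SAP*

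**What the plan says.** Section 4.8.1.2 of the SAP has two steps. The first source is the pill count: "Add-back therapy compliances from the study treatment accountability page will be summarized on the extension treatment period by treatment group". The diary is a fallback: if the linzagolix/placebo and "Add-back therapy compliances from accountability data are missing, compliance will be computed from daily diary data".

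For the fallback, "Compliance will be computed as the number of days with pink tablet/grey tablet/red capsule taken", multiplied by 100 and "divided by the number of days in the period (Month 12 visit date/discontinuation date - Month 6 visit date"). A missing answer for *Today* may be filled from a *Yesterday* item. When neither is available, "it will be assumed that no drug was taken on that day". The section lists no exceptions.

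Appendix A (section 7.1) sets out how diary records filed under the wrong schedule are remapped. Case 2 in Tables 5 and 6 is a woman included in the extension whose diary was "rescheduled to MAIN FU (due to site error in diary completion". Her diary records are moved from MAIN FU to EXT TREAT from the first extension dose onward. The entry for her IMP-intake data is "n/a - missing in final DB" for both devices.

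**The concern.** The two parts of the SAP do not fit together. Appendix A treats the case 2 days as extension treatment days and records that their intake data do not exist. Section 4.8.1.2 then keeps each of those days in the denominator and gives it zero in the numerator.

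Scoring an unanswered day as not taken is a defensible conservative rule when the woman was asked and did not answer. In case 2 the drug-free follow-up schedule was running. The neighbouring cases support the reading that this schedule carries no intake question. Case 1 women, whose diary stayed on the treatment schedule, keep their intake data through mapping. Case 4 women, who entered follow-up with the diary still on the treatment schedule, have intake data that must be deleted. The gap in case 2 therefore comes from the site's scheduling error and says nothing about adherence.

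At stake is the reading of Table 14.1.11.1 (exposure and compliance) and Listing 16.2.5.3 (treatment compliance). The study was terminated early with few subjects, and adherence is part of the background against which the safety tables are read.

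**Working it through.** The plan states no compliance figure, so there is none to reproduce. What can be checked is the period and then the formula.

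**Period.** A month is 28 days counted from Day 1 of the main study (Protocol 10.2; SAP Table 3). Month 6 is Day 1 + 6 × 28 = Day 169, and Month 12 is Day 1 + 12 × 28 = Day 337. The denominator is 337 − 169 = 168. The first extension dose is taken at the Month 6 visit and the last on the day before Month 12 (Protocol 10.2.1), so dosing runs from Day 169 to Day 336, which is 168 days. Denominator and dosing days agree for a woman on schedule.

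**Formula.** Let *d* be the number of days with no intake data from either diary item because the schedule was wrong. For a woman who took every dose, SAP compliance = 100 × (168 − *d*)/168. With those days removed from the denominator it is 100 × (168 − *d*)/(168 − *d*), undefined at *d* = 168. The documents do not give *d*, so a range is shown.

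| *d* (assumed) | SAP 4.8.1.2 | case 2 days excluded |
|---|---|---|
| 0 | 100% | 100% |
| 7 | 161/168 = 95.8% | 100% |
| 14 | 154/168 = 91.7% | 100% |
| 28 | 140/168 = 83.3% | 100% |
| 56 | 112/168 = 66.7% | 100% |
| 84 | 84/168 = 50.0% | 100% |
| 168 | 0/168 = 0% | missing |

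**Sensitivity.**
- Visit windows: with Month 6 and Month 12 each up to 3 days off, the period is 162 to 174 days, and *d* = 28 gives 134/162 = 82.7% to 146/174 = 83.9%.
- Imperfect adherence: a woman who truly took 90% of doses, evenly spread, scores 0.9 × 140/168 = 75.0% at *d* = 28 and 0.9 × 84/168 = 45.0% at *d* = 84. With the exclusion she scores 90% in both.
- Shorter exposure: section 2.1 reports all subjects whatever their treatment duration. Over an assumed 84 days, *d* = 28 gives 56/84 = 66.7%.

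**Effect on an arm mean.** One fully adherent woman affected for *d* of 168 days lowers the mean of an arm of *n* by (100 × *d*/168)/*n* points. Arm sizes are not given. For assumed *n* = 5, 10 and 20, the loss is 3.3, 1.7 and 0.8 points at *d* = 28, and 20, 10 and 5 points at *d* = 168.

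**The case against.** The case for leaving the rule alone is substantial. The accountability page comes first. Blister counts are scheduled at every treatment visit with a final count at Month 12 (Protocol 10.2.1), use of each dose by each subject is to be recorded (11.5), and the monitor checks packages and empty blisters (11.7). A woman is affected only if her accountability compliance is missing and her diary was also mis-scheduled, and no document shows anyone with both. Diary completion is checked at each visit and remotely throughout (Protocol 10.3.1), so a wrong schedule might be caught early. Little hangs on the result: compliance defines no analysis set (SAP 3.1), is not among the listed major deviations (3.2), and does not enter treatment duration, which uses dates (4.8.1.1). Medians and quartiles are reported with the mean (4.2.1), and compliance is listed by subject.

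Most of this stands, and it limits the size of the point. It does not repair the rule. The SAP plans for missing accountability data, and these are plausible: the count depends on women bringing packages to visits (Protocol 11.7), while remote visits and shipped drug were used during the pandemic (5.7). Nothing in the SAP says the listing will show that a low percentage came from a diary error.

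A further objection is that Tables 5 and 6 give case 2 a start date but no end date, so the days cannot be identified. They can: a case 2 day is one whose diary record sits in the MAIN FU data on or after the first extension dose, and the mapping step already has to find those records.

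The shortened *Yesterday* wording in 4.8.1.2 might be read as filling a day with the previous day's answer. Sections 3.1 and 4.2.8.2 settle this: *Yesterday* "of the following day will be considered". That is an editorial matter.

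**Conclusion.** The point holds in a narrow form. Where accountability compliance is missing and the woman falls in case 2, section 4.8.1.2 converts days on which intake could not be recorded into missed doses. A fully adherent woman loses 16.7 percentage points for each 28 such days out of 168. The figures rest on an on-schedule 168-day period, on full adherence unless stated otherwise, and on assumed values of *d* and of arm size.

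A reader might infer more than this. One inference is that compliance in this study is broadly understated, or that adherent women will appear at 0%. The documents do not support it: the diary is a fallback, Tables 5 and 6 define types of error without counts or durations, and 0% requires the wrong schedule for the entire period. Another is that compliance is one of the few analyses left. It is not: Appendix B lists a long set of safety tables, of which compliance is part of one. A third is that safety results or analysis sets are distorted. The rule in 4.8.1.2 feeds neither, and no hypothesis test is planned.

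Section 3.1 applies the same not-taken rule when deriving actual treatment, with the diary as its named source. A woman with no intake data would have zero days on every treatment there. No document shows that such a woman exists, so no misallocation is claimed, but the two sections should handle these days alike.

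**What to change.** In section 4.8.1.2, add that days whose diary record was mapped from MAIN FU to EXT TREAT under case 2 of Tables 5 and 6 are excluded from the denominator, that diary compliance is set to missing if no days remain, and that the number of evaluable days is reported with the percentage. Keep the not-taken rule for days on which the intake question was available and left unanswered, so ordinary non-completion is not excused. A day within a mis-scheduled stretch with no diary entry at all leaves no mapped record, so the sentence should say how it is handled.

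Make the same case 2 exception in section 3.1. As an editorial alignment, restore the following-day wording for the *Yesterday* item in 4.8.1.2.

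The cost is a sentence or two in each section and a flag that the mapping step can supply. The downside is that a woman with neither accountability data nor diary intake data has no compliance value, which is an accurate description of what is known about her.
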